### **13.7.2 Safety**

Safety assessments will be based mainly on the nature, frequency, relationship, and severity of adverse events (AEs). AEs will be coded by primary system organ class (SOC) and preferred term (PT) according to the Medical Dictionary for Regulatory Activities (MedDRA). The treatment-emergent adverse events (TEAEs) will be summarized by the number and percentage of subjects in each SOC and PT. For summaries by relationship to study drug, “possibly related” will be combined with “related”, and “unlikely/remotely related” will be combined with “not related.” When multiple AEs are reported with the same preferred term, the AE of the strongest relation will be included in summary by relationship, and the AE of the most severe grade will be included in the summary by severity table.

All AEs will be listed with onset/stop day, relationship to study drug, severity, action taken, and outcome. Pertinent subject information including cohort and demographics will also be included. Separate listings will be provided for TEAEs leading to study discontinuation and Treatment-emergent serious AEs (TESAEs).

Laboratory data will be summarized by presenting summary statistics of raw data and change from baseline values (means, medians, standard deviations, ranges) and by presenting number and percentage of subjects with notable laboratory abnormalities.

Data from other tests (vital signs) will be listed, notable values will be flagged, and any other information collected will be listed as appropriate.

All safety and tolerability endpoints will be summarized. Baseline for all safety endpoints will be defined as the last recorded observation before the administration of AK002.

### **13.8 Sample Size Calculation**

There is no formal statistical hypothesis testing specified for this study; this study is primarily designed to begin the characterization of the effect and safety and tolerability profile of AK002 in subjects with CU. However, a total of 40 patients is typical for a first-in-indication study and should be adequate to pick up major safety signals should such signals indeed exist.

## **14. Data Collection, Retention and Monitoring**

### **14.1 Data Collection Instruments**

All staff at the study site will adhere to Good Documentation Practices. Data will be entered into CRFs using source document data. Source documents may include, but are not limited to laboratory data, recorded data from automated instruments, medical progress notes, and e-mail correspondence.

### **14.2 Data Management Procedures**

Data collection will be performed in accordance with Good Documentation Practices. Data will be entered into eCRFs using source document data. Source documents may include, but are not limited to laboratory data, recorded data from automated instruments, medical progress notes, and e-mail correspondence. The standard procedures for handling and processing records will be followed per GCP and the data management standard operating procedures. A comprehensive Data Management Plan will be developed and approved by the Sponsor.

### **14.3 Data Quality Control and Reporting**

After data have been entered into the study database, a system of computerized data validation checks will be implemented and applied to the database on a regular basis. Queries are entered, tracked, and resolved through the electronic data capture system directly. The study database will be updated in accordance with the resolved queries. All changes to the study database will be documented.

### **14.4 Archiving of Data**

The database is safeguarded against unauthorized access by established security procedures; appropriate backup copies of the database and related software files will be maintained.

Databases are backed up by the database administrator in conjunction with any updates or changes to the database.

## **14.5 Availability and Retention of Investigational Records**

In accordance with 21 CFR 312.62(c) and ICH/GCP 4.9.5 and all other applicable regulatory requirements, following completion or termination of the study, copies of all study records with limited access storage room, will be retained for a minimum of 2 years after notification that the investigations have been discontinued and the FDA has been notified, or for 2 years after all marketing applications have been approved.

The trial master file will be created during the implementation phase of a study, maintained on an ongoing basis throughout the duration of the project and collated at the end of the study. The files will contain folders that may include, but are not limited to, the following subcategories:

- Financial agreements
- Regulatory documents
- Independent ethics committee (IEC) Documents
- Drug Accountability
- Correspondence
- Medical Reports
- Patient Data
- Monitoring Visit Reports
- Sample CRFs and CRF

## **14.6 Data Monitoring**

Monitoring visits will be conducted by representatives of the Sponsor according to the United States CFR Title 21 Parts 50, 56, and 312 and ICH Guidelines for GCP (E6). By signing this protocol, the Investigator grants permission to the Sponsor (or designee), and appropriate regulatory authorities to conduct on-site monitoring and/or auditing of all appropriate study documentation.

## **14.7 Patient Confidentiality**

Only the patient number, patient initials, and demographics will be recorded in the eCRF. If the patient name appears on any source document collected by the Sponsor (e.g., hospital discharge summary), it must be removed from the document and the patient number and patient initials recorded on the source document before the document is transmitted to the Sponsor. All study findings will be stored in electronic databases. The subjects will give explicit written permission for representatives of the Sponsor, regulatory authorities, and the IEC to inspect their medical records to verify the information collected. Subjects will be informed that all personal

information made available for inspection will be kept confidential and to the extent permitted by all applicable state, local, and federal data protection/privacy laws and/or regulations and will not be made publicly available. If the results of the trial are published, the patient's identity will remain confidential.

All study subjects will be advised not to share their study information with other subjects.

## **15. Administrative, Ethical, and Regulatory Considerations**

The study will be conducted in a manner consistent with the Declaration of Helsinki, Protection of Human Volunteers (21 CFR 50), IEC (21 CFR 56 and ICH E6), and Obligations of Clinical Investigators (21 CFR 312 and ICH E6). The Investigator must also comply with all applicable privacy regulations (e.g., the Health Insurance Portability and Accountability Act [HIPAA], European Union Data Protection Directive 95/46/EC).

### **15.1 Protocol Amendments**

An amendment must be agreed to in writing by Allakos, Inc. and submitted to the health authority as a Clinical Trial Application/Investigational New Drug (IND) amendment. Protocol amendments cannot be implemented without prior written IEC approval except as necessary to eliminate immediate safety hazards to subjects. Written approval of a protocol amendment is not required prior to implementation of changes to the protocol that eliminate immediate hazard to the patient; however, approval must be obtained as soon as possible thereafter. Any agreed amendments must also be signed by the Principal Investigator.

### **15.2 Institutional Review Board/Independent Ethics Committees**

The protocol and ICF will be reviewed and approved by the IRB/IEC of each participating center prior to study initiation. All SAEs, regardless of causality, will be reported to the IEC in accordance with the standard operating procedures and policies of the IRB/IEC, and the Investigator will keep the IRB/IEC informed as to the progress of the study. The Investigator will obtain assurance of IRB/IEC compliance with regulations.

Any documents that the IRB/IEC may need to fulfill its responsibilities (such as protocol, protocol amendments, Investigator's Brochure, ICFs, information concerning patient recruitment, payment or compensation procedures, or other pertinent information) will be submitted to the IRB/IEC. The IRB/IEC's written unconditional approval of the study protocol and the ICF will be in the possession of the Investigator before the study is initiated. The IRB/IEC's unconditional approval statement will be transmitted by the Investigator to Allakos, Inc., prior to the shipment of study supplies to the site. This approval must refer to the study by exact protocol title and number and should identify the documents reviewed and the date of review.

Protocol and/or informed consent modifications or changes may not be initiated without prior written IRB/IEC approval except when necessary to eliminate immediate hazards to the subjects or when the change(s) involves only logistical or administrative aspects of the study. Such modifications will be submitted to the IRB/IEC and written verification that the modification was submitted and subsequently approved should be obtained.

The IRB/IEC must be informed of revisions to other documents originally submitted for review; serious and/or unexpected adverse experiences occurring during the study in accordance with the standard operating procedures and policies of the IRB/IEC; new information that may affect adversely the safety of the subjects of the conduct of the study; an annual update and/or request for re-approval; and when the study has been completed.

### **15.3 Informed Consent Form**

Prior to screening, all subjects must consent to participate.

In accordance with ICH GCP Guidelines E6 Section 4.3.3, subjects will be asked whether or not they would like their PCP notified of their study participation.

The process of obtaining the informed consent will be in compliance with all federal regulations, ICH requirements, and local laws.

The Investigator or a designee will review the study and the ICF with each patient. The review will include the nature, scope, procedures, and possible consequences of the patient's participation in the study. The consent and review must be in a form understandable to the patient. The Investigator or designee and the patient must both sign and date the ICF after review and before the patient can participate in the study. The patient will receive a copy of the signed and dated form, and the original will be retained in the site's study files. The Investigator or designee must emphasize to the patient that study participation is entirely voluntary and that consent regarding study participation may be withdrawn at any time without penalty or loss of benefits to which the patient is otherwise entitled.

In addition, prior to undergoing biopsies, subjects will provide informed consent in accordance with the standard operating procedures and policies of the investigational sites.

### **15.4 Publications**

The preparation and submittal for publication of manuscripts containing the study results shall be in accordance with a process determined by mutual written agreement among the study Sponsor and authors. The publication or presentation of any study results shall comply with all applicable privacy laws, including, but not limited to, HIPAA.

## **15.5 Clinical Trial Registration**

This clinical trial will be registered on the “clinicaltrials.gov” clinical trial registry website as required by 121 STAT. 823.

## **15.6 Payment to Subjects**

All subjects may be compensated for participating in this study, in accordance with the payment amounts per study day stated in the patient’s signed ICF approved by the local IRB/IEC. No compensation beyond what is stated in the ICF is permitted.

## **15.7 Investigator’s Responsibilities**

By signing the Agreement of Investigator form, the Investigator agrees to:

- 1) Conduct the study in accordance with the protocol and only make changes after notifying the Sponsor (or designee), except when to protect the safety, rights or welfare of subjects.
- 2) Personally conduct or supervise the study (or investigation).
- 3) Ensure that the requirements relating to obtaining informed consent and IEC review and approval meet federal guidelines.
- 4) Report to the Sponsor or designee any adverse events that occur in the course of the study, in accordance with 21 CFR 312.64 and ICH E2A.
- 5) Ensure that all associates, colleagues and employees assisting in the conduct of the study are informed about their obligations in meeting the above commitments.
- 6) Maintain adequate and accurate records in accordance with 21 CFR 312.62 and ICH E6 and to make those records available for inspection with the Sponsor (or designee).
- 7) Ensure that an IEC that complies with the requirements of 21 CFR part 56 and ICH E6 will be responsible for initial and continuing review and approval of the clinical study. Promptly report to the IEC all changes in the research activity and all unanticipated problems involving risks to subjects or others (to include amendments and IND safety reports).
- 8) Seek IEC approval before any changes are made in the research study, except when necessary to eliminate hazards to the subjects.
- 9) Comply with all other requirements regarding the obligations of clinical Investigators and all other pertinent requirements listed in 21 CFR Part 312.

## 17. Appendices

### 17.1 Appendix 1: Sampson's Criteria for Anaphylaxis

**ANAPHYLAXIS:** Sampson's definition of anaphylaxis (clinical definition) is the acute onset of illness (minutes to several hours) which involves **SKIN, MUCOSAL TISSUE, or BOTH** (e.g., generalized hives, pruritus or flushing, swollen lips- tongue uvula) **with 1 OR more of the following (Sampson, 2006):**

- **RESPIRATORY:** Airway compromise (e.g., dyspnea, wheeze, or bronchospasm, stridor, reduced PEF, hypoxemia)
- **CIRCULATORY:** Reduced blood pressure or associated symptoms of end-organ dysfunction (e.g., hypotonia, syncope)

**OR**

**2 or MORE of the following that occur rapidly after exposure:**

- **SKIN, MUCOSAL TISSUE:** e.g., generalized hives, itch-flush, swollen lips-tongue-uvula
- **RESPIRATORY:** Airway compromise (e.g., dyspnea, wheeze, or bronchospasm, stridor and reduced PEF)
- **CIRCULATORY:** Reduced blood pressure or associated symptoms of end-organ dysfunction (e.g., hypotonia, syncope)
- **GASTROINTESTINAL:** Persistent gastrointestinal symptoms (e.g., crampy abdominal pain, vomiting, nausea, diarrhea)

## 17.2 Appendix 2: Procedures for Extended Dosing (Optional)

### Summary of Extended Dosing

Subjects in the CholU, UF, and CSU-XOLAIR® (omalizumab) failure cohorts who received all 6 infusions of AK002, were followed through Day 155, and demonstrated severe symptoms of urticaria following discontinuation of treatment will be allowed the option to receive extended dosing with up to 12 additional doses of AK002.

For extended dosing, subjects must have a baseline (Day 1) UCT of  $\leq 5$  and a week 22 (Day 155) UCT of  $\geq 12$  (Complete Response). They must have a UCT of  $\leq 5$  between Day 155 and Day 309 (i.e., within 6 months from last dose). All subjects that decide to receive the extended dosing will start with a dose of 0.3 mg/kg, followed by possible dose increases to 1 mg/kg and 3 mg/kg for subsequent infusions. The Investigator in consultation with the Medical Monitor may increase the dose to 6 mg/kg and then to 10 mg/kg if they think that the patient has not received benefit from the lower doses.

Extended dosing will include a Screening Period of 2 to 3 weeks, a Treatment Period of 44 weeks, and a Follow-up Period of 8 weeks after the last dose of study drug. During the Screening Period, subjects will receive a standard oral dose of a second-generation H1-antihistamine once daily, with on-demand dosing of up to 3 additional tablets per day. During the Treatment Period, subjects will continue daily dosing with the second-generation H1-antihistamine (standard dose once daily with on-demand dosing of up to 3 additional tablets per day) and AK002 administered by IV infusion on Extended Dosing Days 1, 29, 57, 85, 113, 141, 169, 197, 225, 253, 281, and 309. Subjects will be followed for 8 weeks after the last dose of study drug (Follow-up Period). Safety assessments and response to study drug will be evaluated throughout the study. The optional extended dosing period is outlined in [Table 8](#).

**Table 8 Extended Dosing Period**

Description	Screening Period	Treatment Period AK002 Dose (mg/kg) †												Follow-up Period
		0.3	1	1	3*	3*	3*	3*	3*	3*	3*	3*	3*	
Visit	1	2	3	4	5	6	7	8	9	10	11	12	13	14
Week	-3 to -2	0	4	8	12	16	20	24	28	32	36	40	44	52
Extended Dosing Day	-21 to -14	1	29	57	85	113	141	169	197	225	253	281	309	365

\* Increase to 3 mg/kg if UCT score is <12 and/or at the discretion of the Investigator in consultation with the Allakos Medical Monitor. If UCT score is  $\geq 12$ , and if the Investigator in consultation with the Allakos Medical Monitor thinks that the subject has experienced adequate symptom improvement, then continue with the 1 mg/kg dose. The Investigator in consultation with the Medical Monitor may increase the dose to 6 mg/kg and then to 10 mg/kg if they think that the patient has not received benefit from the lower doses.

† The Investigator in consultation with the Allakos Medical Monitor, can chose to maintain the patient's last administered dose depending on how much time has lapsed between Week 20/last dose under main study and first dose under extension.

Based on the subject's weight, the designated clinical staff will prepare the appropriate dilution of AK002 for IV administration at 0.3 mg/kg for Extended Dosing Day 1, 1 mg/kg for Extended Dosing Days 29 and 57, and either 1 mg/kg or 3 mg/kg (depending on UCT score and Investigator discretion) for Extended Dosing Days 85, 113, 141, 169, 197, 225, 253, 281, and 309.

The Investigator in consultation with the Allakos Medical Monitor, can chose to maintain the patient's last administered dose depending on how much time has lapsed between Week 20/last dose under main study and first dose under extension.

The Investigator in consultation with the Medical Monitor may increase the dose to 6 mg/kg and then to 10 mg/kg if they think that the patient has not received benefit from the lower doses.

## Objective

To evaluate the long-term safety and tolerability of up to 12 additional doses of AK002 in subjects with CU.

## Entry Criteria

### Inclusion Criteria

- 1) Adults ( $\geq 18$  and  $\leq 85$  years old)
- 2) Body weight  $< 125$  kg
- 3) Provide signed and dated informed consent
- 4) Enrolled in either the CU, UF, or CSU-XF cohorts
- 5) Completed 6 infusions of AK002 and with follow-up through Day 155 [Week 22]) and willing to begin extended dosing upon qualification
- 6) Must have a baseline (Day 1) UCT of  $\leq 5$  and a week 22 (Day 155) UCT of  $\geq 12$  (Complete Response). They must have a UCT of  $\leq 5$  post-week 22 (Day 155) and by week 44 (Day 309) i.e., within 6 months from last dose.
- 6) Uncontrolled CU (UCT  $< 12$ ) for at least 2 weeks prior to the time of enrollment into the extension
- 7) Able to read, understand, and willing to sign the informed consent form and comply with study procedures
- 8) Willing, committed, and able to return for all clinic visits and complete all study-related procedures, including willingness to have IV infusion of study drug administered by a qualified person
- 9) Females of childbearing potential must have a negative pregnancy test at Baseline. Female subjects must be willing to use highly effective contraception (Pearl-4 Index  $< 1$ ) or abstain from sexual activity from screening until the end of the study, or for 120 days following the last dose of study drug, whichever is longer. A woman will be considered not of childbearing potential if she is post-menopausal for greater than 2 years (FSH  $> 40$  mL) or surgically sterile (bilateral tubal ligation, bilateral oophorectomy, or hysterectomy).  
Male subjects with female partners of childbearing potential must agree to use a highly effective method of contraception from screening until the end of the study or for 120 days following the last dose of study drug, whichever is longer. All fertile men with female partners of childbearing potential should be instructed to contact the Investigator immediately if they suspect their partner might be pregnant (e.g., missed or late menstrual period) at any time during study participation.
- 10) No participation in clinical trials 4 weeks before participation in this study

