Centers/Countries	Approximately 4 study centers in the USA and Germany. Only the sites in Germany will participate in the extension study.
Number of Subjects	
N (total) = Approximately 48 subjects with chronic urticaria
 
This will include the following cohorts:
 
 
• Approximately 12 subjects with Cholinergic urticaria (CholU)
 
• Approximately 12 subjects with Urticaria factitia (UF)
 
• Approximately 12 XOLAIR® (omalizumab) naïve subjects with Chronic spontaneous urticaria (CSU)
 
• Approximately 12 subjects with Chronic spontaneous urticaria (CSU) who did not achieve an adequate response on XOLAIR® (omalizumab) in the opinion of the Investigator
 
 
The extended dosing will be applicable only to the subjects in the CholU, UF, and CSU-XOLAIR® (omalizumab) failure cohorts.

Rationale for Sample Size	The planned sample size of approximately 48 subjects is based on common practice in early phase, proof-of-concept studies.
Duration of Patient Participation and Duration of Study	
The total study duration for each patient will be approximately 32 weeks. This includes:
 
 
• A screening period of 4 weeks prior to study drug administration
 
• Administration of study drug at Day 1, Day 29, Day 57, Day 85, Day 113, and Day 141
 
• Follow-up through Day 197 (8 weeks post last dose)
 

Duration of Patient Participation and Study cont.	Subjects who elect to receive optional extended dosing with up to 12 additional doses of AK002 will participate for up to an additional 12 months (see Appendix 2 ).

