#### 4.2 Secondary Objectives

The effect of AK002 on urticaria symptoms, QOL, provocation testing, and histological criteria

The efficacy, safety and pharmacodynamics of AK002 in CU subjects will be assessed through the following evaluations:

- 1) Safety and tolerability (adverse events, laboratory safety tests, etc.)
- 2) Disease activity scores (UAS7, [REDACTED])
- 3) [REDACTED]
- 4) Number of symptom-free days
- 5) Use of rescue medication (up to 3 sgAH tablets/day)
- 6) Effects on [REDACTED]
- 7) Number of [REDACTED]
- 8) [REDACTED]
- 9) Changes in trigger thresholds (in CINDU, including CholU)
- 10) Rate of [REDACTED] (UCT, [REDACTED]  
[REDACTED])
- 11) Serum levels of potential biomarkers of disease activity and treatment responses
- 12) Rates of relapse and sustained response (during post-treatment follow-up period)

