### **6.1.2 Treatment Period**

During the Treatment Period, all eligible subjects will receive AK002 by IV infusion every 28 days. The first dose will be administered at the beginning of the treatment period Day 1 (Visit 2) after baseline measurements. At Day 141 ( $\pm 2$  days) (Visit 7), the final dose of AK002 will be given. Throughout the treatment period, subjects must maintain stable doses of their baseline AH dose and treatment regimen and remain on a stable treatment regimen through the end of the study. Patient's use of rescue medication will be monitored and reviewed throughout the treatment period and if necessary adjusted according to the current urticaria guidelines ([Zuberbier, 2014](#)). Subjects are expected to attend all site visits based on the assessment schedule (see [Table 3](#)).

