### **6.1.3 Follow-Up Period**

After completion of the Treatment Period, all subjects enter an 8-week follow-up period to obtain further information on the impact of AK002 treatment on urticaria activity and relapse of symptoms. No investigational treatment will be given during the post-treatment Follow-up Period; however, subjects are allowed to take their rescue medication. Rescue medication (a non-sedating antihistamine) will be provided and used on an as-needed basis during the post-treatment Follow-up Period.

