### **6.1.4 Extended Dosing (Optional)**

Subjects in the CholU, UF, and CSU-XOLAIR® (omalizumab) failure cohorts who received all 6 infusions of AK002, were followed through at least through Day 155, and demonstrated severe recurring symptoms of urticaria following discontinuation of treatment (as defined below) will be eligible to receive extended dosing with up to 12 additional doses of AK002 (see [Appendix 2](#)).

To qualify for extended dosing, subjects must have a baseline (Day 1) UCT of  $\leq 5$  and a week 22 (Day 155) UCT of  $\geq 12$  (Complete Response). They must have a UCT of  $\leq 5$  recorded between Day 155 and Day 309 (i.e., within 6 months from last dose).

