6.2 Visit Window and Unscheduled Assessments

There is no visit window for the by visit analysis. Data will be analyzed according to the visit they are associated with.

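### Extended dosing can start before Day 197 under Appendix 2 but not under Section 6.1.3, and the SAP has no Week 28 rule for subjects who start early (minor)

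*Protocol*

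**What the plan says.** **Follow-up.** The last main-study infusion is at Day 141 (Section 6.1.2: "the final dose of AK002 will be given"). The synopsis then plans "Follow-up through Day 197 (8 weeks post last dose". Section 6.1.3 applies this 8-week period to all subjects, gives urticaria activity and relapse as its purpose, and adds: "No investigational treatment will be given during the post-treatment Follow-up Period". Section 4.2, item 12, lists as an objective "Rates of relapse and sustained response (during post-treatment follow-up period".

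**Extension entry.** Section 6.1.4 admits subjects who, among other conditions, "were followed through at least through Day 155". Appendix 2, inclusion criterion 5, reads "Completed 6 infusions of AK002 and with follow-up through Day 155 [Week 22]) and willing to begin extended dosing upon qualification". Entry also needs a Day 1 UCT of 5 or less, a Week 22 UCT of 12 or more, and a UCT of 5 or less recorded between Day 155 and Day 309. No entry criterion mentions Visit 9 or Visit 10. On timing: "Extended dosing will include a Screening Period of 2 to 3 weeks". A further criterion asks for UCT below 12 for at least 2 weeks before extension enrolment, which Appendix 2 equates with the first infusion. The synopsis limits the extension to German sites and to the CholU, UF and CSU-XF cohorts.

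**Analysis.** SAP 7.7.1 and 7.7.1.3 summarise UCT change and the CR, CMR and DC rates by visit, including Week 28. SAP 6.2 sets no visit windows: "Data will be analyzed according to the visit they are associated with". SAP 5.1 applies LOCF to the UCT at Weeks 10 and 22 only. SAP 6.1 removes subjects with missing values from percentage denominators. None of these sections mentions a subject who has already started extended dosing.

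**The concern.** If extended dosing may begin as soon as a subject qualifies, some subjects leave the drug-free period because they relapsed. Their Week 28 UCT is then either absent or taken after AK002 was restarted. Both departures depend on the outcome, and both push the Week 28 summaries in the favourable direction.

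Week 28 matters more than its place as one of eight visits suggests. The UCT looks back 4 weeks, so the Day 169 value covers Days 141 to 169, which is the dosing interval after the sixth infusion. The Day 197 value covers Days 169 to 197. It is the only scheduled UCT whose recall lies wholly beyond one dosing interval after the last dose. The legible SAP endpoints include none for relapse or sustained response, so readers will probably judge durability from the Week 28 tables.

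**Working it through.** **1. The plan's own figure.** From Day 141 to Day 197: (197 − 141)/7 = 8.0 weeks (56 days). This agrees with the synopsis.

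**2. Earliest extension start from a scheduled visit.** First extension infusion = day of the qualifying UCT + 14 to 21 days of screening. The 2-week rule on UCT below 12 is compatible with the same 14-day minimum.
- Qualifying UCT at Visit 9, Day 169: 169 + 14 = Day 183; 169 + 21 = Day 190.
- Days before Visit 10: 197 − 183 = 14; 197 − 190 = 7.
- Days off drug: 183 − 141 = 42; 190 − 141 = 49, against 56 planned.
- With the ±2-day window on Visit 9 (Days 167 to 171), the start falls on Day 181 to 192, with 40 to 51 days off drug.

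**3. Who can be affected.** A start by Day 196 needs a qualifying UCT by Day 182 (196 − 14) or Day 175 (196 − 21). Visit 9 is the only scheduled visit after Day 155 inside that limit. The subject must fall from at least 12 to at most 5, a drop of 7 points or more, between two UCTs 14 days apart whose 28-day recalls share 14 days. Three cohorts of about 12 (about 36 of 48 subjects) are eligible before the site, Day 1 UCT and Week 22 UCT conditions are applied.

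**4. Effect on the Week 28 summaries (assumed outcomes, not from the documents).** Take a cohort of 12: eight subjects at +9 points and in CR at Week 22, and four at 0. Let k of the eight fall back to baseline by Day 169, start the extension, and have no main-study Week 28 value. The others do not change.
- Mean change with all subjects off drug: 9(8 − k)/12. As reported: 9(8 − k)/(12 − k).
- CR rate with all subjects off drug: (8 − k)/12. As reported: (8 − k)/(12 − k).

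| k | Mean, all 12 | Mean, reported | CR, all 12 | CR, reported |
|---|---|---|---|---|
| 0 | 72/12 = 6.0 | 6.0 | 8/12 = 66.7% | 66.7% |
| 1 | 63/12 = 5.25 | 63/11 = 5.7 | 7/12 = 58.3% | 7/11 = 63.6% |
| 2 | 54/12 = 4.5 | 54/10 = 5.4 | 6/12 = 50.0% | 6/10 = 60.0% |
| 3 | 45/12 = 3.75 | 45/9 = 5.0 | 5/12 = 41.7% | 5/9 = 55.6% |

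At k = 2 the mean is overstated by 0.9 points, against the plan's clinically relevant change of 3. The exact 95% interval is 21.1% to 78.9% for 6/12 and 26.2% to 87.8% for 6/10, so the shift of 10 percentage points is small beside the sampling error of one cohort.

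**The case against.** **Section 6.1.3 forbids it.** A reader might infer that the protocol plainly permits re-dosing in the follow-up period. It does not: Section 6.1.3 bars it. What stands is an unresolved conflict, because the entry criteria stop at Day 155 and tie the start to qualification.

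**Visit 10 may already be covered.** Section 9.1 treats leaving the study before Week 28 as early termination. Section 10 then asks for the final-visit assessments, and Table 3 combines the Visit 10 and early-termination columns. Table 9 schedules UCT, diary, pre-dose ADA and pre-dose CBC at the extension baseline visit. This has weight. But nothing says that moving into the extension counts as early termination, the UCT in Table 9 is not marked pre-dose, and no text assigns these values to the main study.

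**The relapse is observed.** A reader might infer that early relapsers vanish from the relapse count. They do not. The qualifying UCT of 5 or less is recorded inside the follow-up period, which is the period named in the objective, and no document defines a relapse rate at Week 28. What is lost is the later off-drug course and a complete Week 28 summary.

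**Re-treatment could restore response by Week 28.** A reader might infer this too, but the documents give it little support. With a restart on Day 183 to 190, 14 to 21 of the 28 recall days (169 to 197) precede the infusion. Appendix 2 also holds extension data on separate eCRFs and in a separate database. A missing value is more likely than one taken on drug.

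**Few subjects, low stakes.** This stands. The primary endpoint is at Week 22, the study tests no hypothesis, and the entry conditions are narrow. Later relapsers, CSU omalizumab-naïve subjects, US subjects and those with a Day 1 UCT of 6 to 11 keep the full 8 weeks, so it would be wrong to say that the subjects who inform the relapse objective are generally lost.

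**Conclusion.** The point holds as a minor one. Section 6.1.3 conflicts with Section 6.1.4 and Appendix 2 on whether extended dosing may start before Day 197, and the SAP is silent on the Week 28 data of a subject who starts early. Followed as written, the SAP would summarise Week 28 without the early severe relapsers, so UCT change and response rates would be somewhat too favourable. The size depends on how many subjects qualify at about Visit 9, which the documents do not allow one to estimate. On the assumed outcomes, one to three such subjects in a cohort of 12 raise the mean change by about 0.5 to 1.25 points and the CR rate by about 5 to 14 percentage points. Two in one cohort is already a demanding assumption. The Week 22 results and the record of the relapse are unaffected.

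**What to change.** 1. **Protocol.** The sponsor should reconcile Section 6.1.3 with Section 6.1.4 and Appendix 2 on whether extended dosing may start before Day 197. This review takes no position on which rule is right.
2. **Appendix 2.** For any subject who does start earlier, record the Visit 10 assessments (UCT, diary, ADA, biomarkers) before the first extension infusion, as the end of main-study follow-up.
3. **SAP.** State that no value obtained after an extension infusion is analysed as main-study Week 28. For these subjects, use the pre-infusion UCT in the Week 28 change summary, keep them in the Week 28 denominator as non-responders for CR, CMR and DC, and report the number of early starters by cohort. A footnote should say that the substituted UCT was taken before Day 197.

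The cost is one sentence in Appendix 2, whatever edit the reconciliation needs, and a few sentences in the SAP. Most of the assessments are already scheduled at the extension baseline visit; the UCT would need to be marked pre-dose and any biomarkers outside the CBC added. The drawback for the sponsor is that the Week 28 results may look slightly less favourable.
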